3.2.4. Exploratory Outcome Measures

- Time from randomization to initial clinical improvement in Norovirus disease through 28 and 180 days for at least 48 hours, as defined by:
 - 50% reduction in number of episodes of vomiting and,
 - Improvement in PO intake, as judged by the subjects and,
 - 50% reduction in the number of episodes of diarrhea as classified by the subject by the Bristol Stool Chart as type 6 or 7 bowel movements.
- Time from randomization to initial cessation of vomiting through Day 180 (recurrent vomiting will be considered disease recurrence unless determined to be due to another etiology [i.e. GVHD]).
- Time from randomization to subject report of no loss of appetite that is maintained for 48 hours through Day 180 (measure will be first time that the subject reports that they have no “loss of appetite” on their daily diary).
- Time from first dose to initial cessation of diarrhea through Day 180 classified by the Bristol Stool Chart as type 6 or 7 bowel movements (recurrent diarrhea will be considered disease recurrence unless determined to be due to another etiology [i.e. GVHD]).
- Time from randomization to 50% reduction in the amount of antimotility agents utilized by the subject through Day 180.
- Number of days of diarrhea through Days 28 and 180.
- Number of stools classified by the Bristol Stool Chart as type 6 or 7 bowel movements through Day 28.
- Number of days of IV hydration or total parenteral nutrition (TPN) therapy through Day 28.
- Total number of days of hospitalization through Days 28 and 180.
- Change in patient-reported quality of life as measured by EuroQOL-5 (global) and IBSQOL (diarrhea specific) [adult] or EuroQOL-5 Peds (global) and PedsQL GI Module [children] from baseline to Day 180.
- Change in patient-reported physical function as measured by NIH PROMIS Physical Function (Adult) Pediatric Global Health (Peds) from baseline to Day 180.
- Change in patient-reported emotional distress as measured by the NIH PROMIS Depression, Anxiety, Fatigue (Adult and Peds) from baseline to Day 180.
- Change in patient-reported gastrointestinal symptoms as measured by the NIH PROMIS GI (Adult and Peds) symptoms (6 of 8 subscales) from baseline to Day 180.
- The effect of co-pathogens, as determined by the BioFire stool pathogen screen, on the primary outcome measure.

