2	49.3
3	52.9
4	55.9
5	58.7
6	60.9
7	62.8
8	64.6
9	66.4
10	68.1
11	69.8
12	71.6
13	73.5
14	75.6
15	78.0
16	80.4

Fecal Incontinence:

Raw score	T-score
0	42.0
1	49.1
2	54.4
3	58.6
4	62.1
5	64.4
6	66.0
7	67.7
8	69.5
9	71.4
10	73.5
11	75.8
12	78.4
13	80.8
14	80.8
15	80.8
16	80.8

Belly Pain:

Raw score	T-score
0	31.7
1	37.2
2	40.6
3	43.5
4	46.2
5	48.6
6	50.7
7	52.6
8	54.3
9	55.9
10	57.5
11	59.1
12	60.5
13	61.9
14	63.2
15	64.5
16	65.8
17	67.0
18	68.3
19	69.5
20	70.8
21	72.1
22	73.5
23	74.9
24	76.1
25	76.9
26	77.9
27	78.6
28	78.6
29	82.1

If items are missing, confirm that at least 50% have been answered before calculating the score. If less than 50% of the questions have been answered, the score will be left as missing. If less than 50% of the items are missing, the pro-rated raw score will be:

$$\text{Raw score} = \frac{\text{Raw sum} \times \text{Total number of questions in domain}}{\text{Number of items that were actually answered}}$$

If the result is a fraction, round up to the nearest whole number. Note that only three of the four nausea questions from the GI questionnaire were included, therefore in order to meet the 50% criteria at least 2 of the 3 questions must be answered.

Positive and Negative Affect Scale (PANAS):

Adult subjects will complete the NNITS PROMIS PANAS Questionnaire. Patient-reported positive and negative affect scores will be reported in two separate categories: positive affect score and negative affect score.

The score for positive affect will be the sum of questions #1, 3, 5, 9, 10, 12, 14, 16, 17, and 19. The score for negative affect will be the sum of questions #2, 4, 6, 7, 8, 11, 13, 15, 18, and 20.

Reduction in Amount of Antimotility Agents:

The amount of antimotility agents for a given day will be defined as the response to the “# of antidiarrheals today” question in the Phase 1 (Treatment Phase) Daily Symptom Diary. Missing responses will be left as missing. 50% reduction in the amount of antimotility agents will be defined as the first study day in which the subject’s response was less than or equal to 50% of their response given on Day 1.

Number of Days of Diarrhea:

The number of days of diarrhea will be based on the Daily Diary Diarrhea Questions (see above). For a day to count towards the number of days of diarrhea, one of the following must occur: a quantitative diarrhea question must be greater than 0 or a qualitative question must be marked “yes”. Missing responses will be left as missing.

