Number of Type 6 or 7 Stools:

The number of Type 6 or 7 stools through Day 28 will be defined as the sum of the responses to the quantitative Daily Diary Diarrhea Questions during the Treatment Phase (see above). Missing responses will be left as missing.

Number of Days of IV Hydration or Total Parenteral Nutrition (TPN) Therapy:

The number of days of IV hydration or TPN therapy will be defined as the number of days with a concomitant medication with any indication related to IV hydration or TPN therapy. A blinded review of the concomitant medication data will be performed by the Medical Monitor to identify medications that should be included in the analysis. Days prior to Day 1 will not be included in the calculation of the number of days. Medications that are ongoing after Day 28 will be censored at 28 days.

Co-pathogen Status:

Co-pathogen status will be determined by the BioFire stool pathogen screen on Days 1 and 180. Co-pathogen status will be determined on Days 7, 14, 21, 28, 60, 120, and with recurrent diarrhea if unformed stool is present on study day. Analyses will only include whether pathogens were detected or not and will not differentiate by co-pathogen type. The listing will include which co-pathogens were detected at each subject/visit ([Listing 18](#)).

Secretor Status:

Saliva is collected at screening to determine H type 1 secretor status (phenotyping), while a buccal swab is collected to perform FUT2 genotyping. Phenotype and genotype results will either be “secretor” or “non-secretor” for each subject.

Norovirus-Specific Immunoglobulins (Ig):

Results below the lower limit of detection (LLOD) will be imputed as $\frac{1}{2}$ the LLOD. Results above the upper limit of detection (ULOD) will be imputed as the ULOD.

Responders:

A subject is classified as a responder if he or she has a four-fold or greater increase in Norovirus-specific Ig titers compared to baseline (Day 1).

Study Day:

Study day will be reported as the number of days from randomization with the day of randomization reported as study day 1.

Days Post-Randomization:

Days post-randomization will be reported as the number of days since randomization; if an event began on the day of randomization, the days post-randomization is reported as 0.

Duration:

Duration will be reported as the difference between the start and end dates, inclusive of the day the event started.

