4.4.7. Prior and Concomitant Therapy

Subjects may receive any therapy that is deemed appropriate to treat the signs and symptoms of Norovirus after randomization at the discretion of their treating provider except for nitazoxanide and oral immunoglobulin. This can include:

- Intravenous immunoglobulin
- Changes in immunosuppression
- Anti-motility agents

Any treatment utilized should be included on the concomitant medications at the time of enrollment. Any concomitant medication pre- or post-randomizations that is being used to treat the signs or symptoms of Norovirus should be marked as such on the Case Report Form for the entire duration of the study. Likewise, any change to immunosuppressive therapy would have a note in the Case Report Form noting if the change was made because of elevated drug levels, for treatment of Norovirus or other purposes. Concomitant medications will be collected through visit 12 (Day 180 after initial dose of study treatment) or early termination, whichever occurs first. If the Investigator learns that the subject has taken a prohibited medication (see inclusion/exclusion criteria) prior to the last dose, the Investigator will contact the DMID Medical Officer and CPM for instructions regarding the subject's continuation in the study.

Medications that might interfere with the evaluation of the investigational product should not be used unless absolutely necessary.

If symptoms recur after discontinuing therapy, subjects can resume any therapy at the discretion of the principal investigator or his/her designee with the exception of nitazoxanide. Nitazoxanide can be used after Day 28 if the local PI attests that it is medically urgent to use the nitazoxanide because the patient is experiencing severe or life-threatening disease. Although nitazoxanide can be used if it is felt critical to the subjects care, its use should be avoided until Day 180 whenever felt to be safe to do so by the local PI. Any use of nitazoxanide beyond Day 28 will be documented on the concomitant medication form and prescribed from commercial stock and not provided by the study.

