8.3. Exploratory Efficacy Analyses

The protocol calls for a Log-Rank test at the 5% two-sided level of significance for the following exploratory outcome measures:

- Time from randomization to initial clinical improvement in Norovirus disease through 28 and 180 days for at least 48 hours.
- Time from randomization to initial cessation of vomiting through Day 180 (recurrent vomiting will be considered disease recurrence unless determined to be due to another etiology [i.e. GVHD]).
- Time from randomization to subject report of no loss of appetite that is maintained for 48 hours through Day 180 (measure will be first time that the subject reports that they have no “loss of appetite” on their daily diary).
- Time from randomization to initial cessation of diarrhea through Day 180 classified by the Bristol Stool Chart as type 6 or 7 bowel movements (recurrent diarrhea will be considered disease recurrence unless determined to be due to another etiology [i.e. GVHD]).
- Time from randomization to 50% reduction in the amount of antimotility agents utilized by the subject through Day 180.

However, due to early closure of the study, the number of subjects is too small to use a Log-Rank test. Instead, a stratified Cox proportional hazards model will be used to compare treatment to control through Day 28 and/or Day 180. Stratification is based on acute versus chronic symptoms at baseline. No pediatric subjects were enrolled in the study and only one hematopoietic stem cell transplant subject was enrolled in the study; therefore, the transplant type and age range strata will not be included in the final analysis.

The analysis will be performed in the mITT analysis population. The treatment hazard ratio estimate, 95% confidence interval and p-value from the likelihood ratio test will be presented for each event (Table 29). The median time to event and 95% confidence interval will be summarized by treatment arm and duration of symptoms. In addition, stratum-specific estimates of the treatment hazard ratio within each duration of symptoms strata will be presented. Kaplan-Meier curves for each treatment arm will be displayed in Figure 20, Figure 21, Figure 22, Figure 23, and Figure 24.

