13. TECHNICAL DETAILS

SAS version 9.4 or above will be used to generate all tables, figures and listings or R version 4.1.1 or higher.

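### Under SAP 3.3 a zero entered on Day 1 counts as a 50% antimotility reduction on Day 1; the Day 28 stool total has a related gap that depends on how the diary was filled in

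*SAP*

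**What the plan says.** **Antimotility outcome.** SAP 3.2.4 lists it as "Time from randomization to 50% reduction in the amount of antimotility agents utilized by the subject through Day 180". SAP 3.3 takes the daily amount from the antidiarrheal count, a "question in the Phase 1 (Treatment Phase) Daily Symptom Diary", leaves missing responses missing, and sets the event at the first study day on which the "response was less than or equal to 50% of their response given on Day 1". The same section numbers the day of randomization as study day 1.

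On who is analysed, SAP 8.3 states: "The analysis will be performed in the mITT analysis population". The N in Table 29 is every subject in the arm, duration stratum and population. Antimotility use is not an entry criterion in SAP 4.3, and SAP 4.4.7 says subjects "may receive any therapy that is deemed appropriate to treat the signs and symptoms of Norovirus after randomization at the discretion" of the treating provider, with anti-motility agents among the examples. The same section adds: "Concomitant medications will be collected through visit 12 (Day 180 after initial dose of study treatment) or early termination, whichever occurs first". The event definition does not use that log.

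**Stool total.** SAP 3.3 says the Day 28 number of Type 6 or 7 stools "will be defined as the sum of the responses to the quantitative Daily Diary Diarrhea Questions during the Treatment Phase", and missing responses stay missing. The Treatment Phase diary also has, for each of the two stool types, a tick for too many to count. SAP 6.5 confines imputation to the primary endpoint.

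**The concern.** A subject who takes no antidiarrheals on Day 1 has nothing to halve, yet the rule records success at the earliest possible time. Table 29 and Figure 24 would then mix two things: reduction among users, and the share of non-users at baseline. If more than half of an arm enters 0, that arm's median is Day 1 whatever the drug does. Equal shares of zeros pull the hazard ratio toward 1 on average. With 31 subjects enrolled, a chance imbalance in zeros can move it either way.

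The stated horizon is a second mismatch. The amount is defined only from the Day 1–28 diary, so under this definition no event can be dated after that diary ends, although the outcome is labelled as running to Day 180.

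For the stool total, the concern is that a subject's heaviest days may carry no number. The days-of-diarrhea rule counts a ticked day, and the resolution rule requires the ticks to be blank; the stool total does not use them.

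**Working it through.** The plan gives no figure for either definition, so the check is to apply the rules literally.

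**1. The antimotility rule.** The event is the first day d ≥ 1 with x(d) ≤ 0.5 × x(1).

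| Responses from Day 1 | Threshold | Event day |
|---|---|---|
| 4, 4, 3, 2 … | 2 | Day 4 |
| 1, 1, 1, 0 … | 0.5 | Day 4 |
| 0, 0, 0, 0 … | 0 | Day 1 |
| 0, 4, 4, 6 … | 0 | Day 1, although use rose |
| blank, 4, 2, 0 … | undefined | none |

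A user's own Day 1 value cannot satisfy the rule, since x ≤ 0.5x fails for x > 0. The fault is confined to entered zeros. Restricting to x(1) ≥ 1 leaves every user's event day unchanged.

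**2. Effect on the median (assumed inputs).** Let a share s of each arm enter 0, and let users have exponential times with median m. Solving (1 − s) × exp(−t × ln 2 / m) = 0.5 gives t = m × ln[(1 − s)/0.5] / ln 2. Take m = 10 and 20 days:
- s = 20%: 10 × ln 1.6 / ln 2 = 6.8 and 13.6 days.
- s = 40%: 10 × ln 1.2 / ln 2 = 2.6 and 5.3 days.
- s = 50%: Day 1 in both arms.

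**3. Effect on the hazard ratio (simulation, assumed inputs).** The set-up was 16 versus 15 subjects, users' medians 7 versus 14 days (hazard ratio 2), whole-day times, censoring at Day 28, and an unstratified Cox model with Efron ties.

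| Day 1 zeros | Median HR, SAP rule | Power, SAP rule | Power, users only |
|---|---|---|---|
| 20% | 1.70 | 27% | 34% |
| 40% | 1.46 | 16% | 26% |
| 60% | 1.29 | 9% | 19% |

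Users only gave a median hazard ratio of 2.0 to 2.1. With a true hazard ratio of 1, zeros shifted the estimate by more than a factor of 1.25 upward in 16%, 26% and 34% of trials, and downward in 13%, 25% and 33%.

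**4. The stool total, if a tick has no number.** Compare a subject with 28 days at 5 stools, total 28 × 5 = 140, with one who has 18 such days and 10 ticked days.
- Blanks skipped: 18 × 5 = 90, so the worse subject ranks better in the rank-sum test of Table 30.
- Blanks void the total: that subject drops out.
- Each ticked day valued at 10 (assumed): 90 + 100 = 190, which restores the order.

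If a number accompanies the tick, it is summed and nothing is lost.

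**5. Days with no diary.** The same question of skip or void applies. The compliance limit of 1.5 missed days in 7 allows 28 × 1.5/7 = 6 missed days, or 6/28 = 21% of the sum at a constant daily count. A rule for ticks alone would leave this open.

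**The case against.** **Intent.** The outcome is worded as a reduction in agents actually used, and going from 0 to 0 is not a reduction, so a sensible programmer might exclude non-users anyway. But the SAP definition is what would be programmed, and neither SAP 8.3 nor Table 29 excludes them.

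**Form behaviour.** If non-users leave the item blank, they have no threshold and no Day 1 event. Only an entered 0 triggers the fault, and the documents do not show how often that happened. This stands; it limits what can be said about size, not about the rule.

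**The stool half.** A reader might infer that the stool total is also wrong as written. The documents do not support that. A blank count under a tick is suggested only by the Listing 12 shell, whose example cell shows either a number or the words for too many; the diary form is not in the documents. The resolution rule points partly the other way: it requires both counts to be 0 and both ticks to be absent, and the second condition would be redundant if a tick always left its count blank. This half is a conditional ambiguity.

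**Weight.** The zero shares, medians and arm split are assumed, the simulation is unstratified whereas SAP 8.3 stratifies, and SAP 14.2 calls the analyses primarily descriptive. Power is a weak yardstick for exploratory outcomes in a trial stopped at 31 subjects. That is fair, but a descriptive median should still describe the named quantity.

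**The remedy.** Restricting to Day 1 users drops anyone who starts on Day 2. That is a real cost, but such a subject has no Day 1 amount to halve.

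**Conclusion.** The antimotility definition needs correcting. An entered Day 1 zero is an event on Day 1, by arithmetic that depends on no assumption, and nothing in the analysis population removes it. The Day 180 label also does not match a measure taken only from the Day 1–28 diary.

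The size is unknown. The simulated hazard ratios and powers show direction and plausible scale only, and should not be read as estimates of what happened in this trial. Nor do the documents support inferring that Day 1 zeros were common, or that the fault reaches beyond this outcome: the primary, secondary and safety outcomes do not use it.

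The stool total is a secondary, conditional point. It matters only if ticks were recorded without numbers, and the rule for days with no diary is unstated in any case.

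**What to change.** **Antimotility (SAP 3.3, Table 29, Figure 24).**
- Restrict this analysis to subjects with a Day 1 response of at least 1, and footnote the number excluded by arm.
- Censor subjects without the event at their last Treatment Phase diary.
- Record the departure from the Day 180 wording.

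**Stool total (SAP 3.3, Table 30).**
- Before unblinded analysis, confirm from the form or the data whether ticks come without numbers.
- If they do, assign a value above the highest recorded count for that stool type, as a stated exception to SAP 6.5, and footnote the number assigned by arm.
- State how days with no diary enter the total.
- Keep the exact rank-sum test.

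Naming the Cox tie method is optional. SAP 13 ("SAS version 9.4 or above will be used to generate all tables, figures and listings or R version 4.1.1 or higher") does not name one; in the illustration at 60% zeros, the SAP rule gave a hazard ratio of 1.29 with Efron ties and 1.26 with Breslow.

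**Cost.** The changes are edits to two definitions, a possible exception in SAP 6.5, one recorded departure and table footnotes. No new data or tests are needed. The antimotility analysis has fewer subjects, and under SAP 8 any subgroup with fewer than five subjects per arm would not be shown.
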